3.3 Sample size calculation

Sample size is calculated for the primary outcome 6 minute walking distance (6MWD) measured with 6 minutes walking test (6MWT). A systematic review on measurement properties of field walking tests conducted by the European Respiratory Society and American Thoracic Society(6) found a median minimal important difference (MID) of 30 meters for the 6MWT (range 22-57 meters) across studies using anchor- or distribution-based approaches in different lung disease including COPD, pulmonary arterial hypertension, and interstitial lung disease. Since an MID for 6MWT in COVID-19 has not been established at the time of the development of the TEREKO protocol and learning effects may also occur (particularly in the exercise group), a larger and thus more conservative MID of 50 meters is supposed here. A standard deviation of change in 6MWD over six weeks of 99 meters in controls and 71 in the intervention group as reported in a previous trial on the effectiveness of an exercise program in SARS survivors(3) is further assumed. The assumption of a greater standard deviation in controls makes sense in so far as a greater variety of outcomes can be expected in this group due to greater variations in disease course and environmental influences as these are not influenced by a targeted intervention. With a power of 80% and an alpha error of 5% this yields a sample size of 96 participants respectively 48 per group to detect a statistically significant signal for a difference in change in 6MWD between

groups with an independent samples t-test. This corresponds to power analysis for ANCOVA or constrained longitudinal data analysis for high correlations ($r \geq 0.8$) between repeated measurements(7, 8). An assumption of such high correlation is conservative and justified given that we have no previous knowledge about the effectiveness of similar interventions in the target population. Assuming an attrition rate of 20% the recruitment target is 120 participants or about 60 per group.

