4.1 Confidence intervals and P values

Level of statistical significance is set at alpha error = 0.05. No adjustments for multiplicity are

made. Treatment effects will be reported with 95 % confidence intervals.

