5.1 Eligibility

Inclusion criteria are

- (1) COVID-19 (confirmed SARS CoV-2 infection);
- (2) discharged from hospital-based acute treatment for Covid-19;
- (3) moderate dyspnea symptom (mMRC 2~3);

- (4) aged 18 to 75 years;
- (5) possession of and ability to use smart phone (study subjects or family members);
- (6) provided informed consent and signed the informed consent form.

Exclusion criteria are

- (1) resting heart rate > 100 bpm;
- (2) taking drugs which affect cardiopulmonary function or heart rate (such as: trimetazidine, salbutamol, beta-blocker);
- (3) combined uncontrolled chronic disease, such as uncontrolled hypertension (resting BP \geq 160/100 mmHg), uncontrolled diabetes (random blood glucose > 16.7 mmol/l, HbA1C > 7.0%);
- (4) combined severe organic disease, such as unstable hemodynamic heart disease, heart failure with limited movement (previous diagnosis, or having clinical symptoms of heart failure, after consultation by cardiologist), unstable angina, MI within past 12 months or other cardiac diseases;
- (5) cerebrovascular disease that occurred within the past 6 months;
- (6) active stage of digestive ulcer, thyroid dysfunction, or active tuberculosis;
- (7) chronic kidney disease \geq stage 3 (eGFR < 60 ml/min);
- (8) having received intra-articular drug injection or surgical treatment in lower extremities within past 6 months;
- (9) poor compliance, unable to cooperate with assessment or training; (10) unable to walk independently with auxiliary;
- (11) combined mental disease that prevents patients from living independently or receiving treatment;
- (12) alcohol abuse or illegal drug use history;
- (13) pregnant, nursing or preparing for pregnancy (including male subjects);
- (14) having participated in other clinical trials within the past 3 months or currently enrolled in other clinical trial;
- (15) enrolled in other rehabilitation program.

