As mixed effects models are used for analysis of treatment effects and listwise deletion of cases with missing data is thus avoided, main analysis will be performed on available (unimputed) data, assuming that data are missing at random (MAR) and missing values depend on observed variables in the model (center, time point, and the interaction of group and time point)(21, 22). This assumption will be tested in sensitivity analysis (see below).

Sensitivity analysis and per protocol analysis

Two types of sensitivity analysis will be performed. First, above analyses will be repeated on 50 multiply imputed datasets(23) whereas imputation is based on available outcome data as well as available baseline information including variables not included in the analysis models. This compares the simple MAR assumption outlined above with an extended MAR assumption, i.e. that missing values are also dependent on observed (auxiliary) variables not included in the models used for primary analysis. Apart from center, these auxiliary variables comprise gender, age, disease severity, time from first hospital admission for Covid-19 to baseline assessment, presence of comorbidities, smoking history, and body mass index. Imputation is preferred over adjustment within the mixed models (adding covariates) as conditioning on covariates is not intended given this is a pragmatic trial and to avoid overfitting of the models. Chained equations will be used for simultaneous imputation of all missing outcome data. Second, reference-based multiple imputation will be used for simulating a non-missing at random (NMAR) scenario where patients with missing assessments in the intervention group are supposed to experience change in the outcome that is similar to that observed in the control group after the last available data point before dropout. This is called copy increments in reference (CIR) approach. Imputation is based on a joint multivariate normal distribution of the outcome for each treatment arm. In the case of CIR those in the intervention group are supposed to switch to the distribution of the control group after dropout(24). CIR imputation is done separately for each outcome and considering center and auxiliary covariates specified for extended MAR imputation. Per protocol analysis will also be performed estimating the previously specified models on data including only those participants from the intervention group who had adhered to the TEREKO protocol as defined above.

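### The primary 6MWD analysis is valid but gives up precision: time since admission and disease severity are collected, used only for imputation, and never adjusted for

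*SAP*

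**What the plan says.** - **Entry (SAP 5.1).** Patients must have been "discharged from hospital-based acute treatment for Covid-19" and have mMRC 2 to 3. The list sets no minimum or maximum time since discharge or admission.
- **Randomization (SAP 3.2).** Stratified by study center only.
- **Data collected (SAP 5.3).** Disease severity and the admission and discharge dates are among the baseline data.
- **Primary model (SAP 6.2).** A cLDA of 6MWD on center, time point and time-by-group. Baseline 6MWD is adjusted for implicitly through the constrained baseline mean, and center is the only other adjustment.
- **Use of the two variables (SAP 6.2, sensitivity analyses).** Disease severity and "time from first hospital admission for Covid-19 to baseline assessment" are auxiliary variables in the extended-MAR imputation and again in the CIR imputation. The analysis models are then refitted without them. The reason for imputing rather than adjusting is that "conditioning on covariates is not intended given this is a pragmatic trial and to avoid overfitting of the models".
- **Sample size (SAP 3.3).** "A standard deviation of change in 6MWD over six weeks of 99 meters in controls and 71 in the intervention group" is assumed. The larger control value is explained by "greater variations in disease course and environmental influences".

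**The concern.** The plan treats time since admission and severity as informative enough to improve imputation of missing 6MWD, but not as worth using in the comparison itself. Both are fixed before allocation and could plausibly predict how far a patient improves in six weeks, because two patients with the same baseline distance may be at different stages of recovery. Adjusting for baseline 6MWD does not capture that.

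Neither stated reason fits the linear 6MWD model. Without a treatment-by-covariate term, a baseline covariate leaves the average treatment difference unchanged, so the pragmatic question stays the same. Two prespecified covariates are also few for about 96 evaluable patients. At stake are the width of the confidence interval and the power of the primary comparison, using data the trial already holds.

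**Working it through.** **Inputs**

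- Difference 50 m, SDs of change 99 m (control) and 71 m (intervention), 48 per group, 80% power and 5% alpha: SAP 3.3.
- Two-sided testing is inferred. The SAP does not state it, but two-sided testing reproduces 48 per group, while one-sided testing would need 37.
- Share of the variance of change explained by the two covariates, beyond center and baseline 6MWD (R²): not in the SAP. Assumed 5% to 30%, equal in both arms.

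**1. Reproduce the plan's figure**

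SE = √((99² + 71²)/48) = √(14842/48) = 17.58 m. Welch noncentral-t power at 50 m with 48 per group is 80.3%, and 48 is the smallest size that reaches 80%. 96/0.80 = 120. The sample size in the SAP is correct.

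**2. What baseline 6MWD already removes**

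SAP 3.3 equates its t-test on change with ANCOVA or cLDA for r ≥ 0.8. With equal variances at both visits (a simplification), ANCOVA leaves (1 + r)/2 of the variance of change, which is at least (1 + 0.8)/2 = 90%. On the plan's own correlation, baseline adjustment therefore removes at most about 10%.

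**3. Gain from adjusting**

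SE after adjustment = 17.58 × √(1 − R²); the half-width is 1.96 × SE.

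| R² (assumed) | SE (m) | 95% CI half-width (m) | Power at 50 m |
|---|---|---|---|
| 0 | 17.6 | 34.5 | 80.3% |
| 5% | 17.1 | 33.6 | 82.2% |
| 10% | 16.7 | 32.7 | 84.2% |
| 20% | 15.7 | 30.8 | 88.2% |
| 30% | 14.7 | 28.8 | 91.9% |

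**4. Cost if the covariates are useless**

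For two one-degree-of-freedom covariates, the expected variance inflation is about (96 − 3)/(96 − 5) = 93/91 = 1.022. The SE becomes 17.58 × √1.022 = 17.8 m and power about 79.4%, a loss of 0.9 points. Charging the same cost to the rows above lowers each power by about 0.6 to 0.8 points, for example 84.2% to 83.4% at R² = 10%.

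**5. Is the unadjusted analysis wrong?**

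A simulation of ANCOVA with 48 per group and the SAP's SDs (8000 runs per scenario) used one covariate with correlation rho to change.

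| rho (rho²) | Unadjusted: SD of estimate, power | Adjusted: SD of estimate, power |
|---|---|---|
| 0.3 (9%) | 17.5 m, 80.0% | 16.9 m, 83.2% |
| 0.5 (25%) | 17.7 m, 80.4% | 15.5 m, 89.2% |

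Across rho 0.2, 0.3 and 0.5, the unadjusted mean estimate was 49.7 to 50.3 m when the truth was 50 m, and −0.1 to 0.2 m under the null. Its rejection rate under the null was 4.8% to 5.4%. It is unbiased and holds its level.

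**6. Chance imbalance in the same terms**

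The 95% range of the shift that imbalance can cause is ±1.96 × √R² × 17.58, which is ±7.7 m at R² = 5% and ±10.9 m at 10%. This is one component of the 17.58 m, since 17.58² = R² × 17.58² + (1 − R²) × 17.58². It must not be added to the loss in step 3.

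**The case against.** The strongest reply is that this is a declared and valid choice. Randomization makes the center-only cLDA unbiased, its standard error already allows for imbalance, and the trial is sized for 80% power without these covariates. All of that stands. The gain also rests on an R² that the SAP does not supply, and at 5% it is about 2 points of power.

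Other parts of the reply also stand:

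- The quoted sentence rejects the whole auxiliary list (gender, age, severity, time since admission, comorbidities, smoking, BMI). Overfitting is a fairer worry for seven variables, each with a time interaction, than for two.
- The sentence also covers the longitudinal logistic model for mMRC. There, conditioning on covariates does change the target odds ratio, so the sentence should not simply be deleted.

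A reader might infer three stronger things that the SAP does not support:

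- **That the open entry window makes recovery vary widely.** The SAP gives no figure for time since illness. Entry is narrowed by mMRC 2 to 3, and the protocol, not shown, may set a window. The remark on disease course in SAP 3.3 explains why controls should vary more than treated patients; it also names environmental influences and says nothing about time since discharge.
- **That imbalance biases the result on top of the lost precision.** It is the same variance, counted once.
- **That drop-out related to recovery stage is ignored.** The main analysis assumes it away, but the extended-MAR and CIR analyses include both variables and check it.

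What the reply does not answer is why two prespecified covariates should be excluded from a linear model. Neither stated reason covers that case.

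**Conclusion.** The point holds as a recommended improvement in efficiency. The primary 6MWD analysis is valid and the sample size is correct; nothing here implies bias or an inflated type I error. The SAP forgoes a cheap gain in precision on grounds that do not apply to the linear model. For R² of 5% to 30%, power rises from 80% to between 82% and 92% and the SE falls from 17.6 m to between 17.1 and 14.7 m. If the covariates carry almost no information, the loss is under about 1 point. These figures assume the SAP's SDs, 48 evaluable per group, the same R² in both arms, and one degree of freedom per covariate for the cost. The asymmetry between the small possible loss and the larger possible gain supports adjusting, even though the true R² is unknown.

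**What to change.** In SAP section 6.2:

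1. Add time from first admission to baseline in one form fixed in advance (for example log days) and disease severity, with its categories stated, to the cLDA for 6MWD and the other continuous outcomes. Enter each with its interaction with time point, because a main effect alone does not model different change between baseline and follow-up.
2. Fill any missing covariate values with a simple baseline imputation, so that no patient is dropped.
3. Keep the center-only model as a sensitivity analysis.
4. Limit the sentence rejecting covariates to the longer auxiliary list and the mMRC logistic model.
5. Report time since admission by arm with the baseline characteristics.

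The cost is SAP wording, a few degrees of freedom and a slightly less simple model. The data are already planned. The choice should be fixed before outcome data are seen; adjustment added after an imbalance appears would look data-driven.

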3.1 Design

Pragmatic, multi-center, randomized-controlled, 1:1 parallel group trial. The control group receives educational instructions for daily living at baseline. The intervention group participates in a 6-weeks, home-based, remotely monitored exercise program for cardiopulmonary rehabilitation, delivered via smartphone (R+ health app software) with 3-4 sessions per week and monitored remotely in real-time via a heart rate device worn on the body of the patient. Exercises types include breathing control and thoracic expansion, aerobic exercise, and muscle strength exercises. Exercise difficulty, intensity, and duration is scheduled to increase over time.

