Sub-group analysis

Due to lack of power for this type of analysis, no pre-specified sub-group analysis will be performed.

Analysis of harms

Patients in the intervention group can actively report adverse events to the responsible doctor at any time through the smart phone app or contact the responsible doctor, clinical department, or

researcher by phone or WeChat. Patients in the control group can actively report adverse events by contacting the responsible doctor, the clinical department, or the researcher by phone or WeChat. In addition, all patients will be asked at 2 and 4 weeks telephone consultations, at the 6 weeks post-treatment assessment and at 24 weeks follow-up assessment if any adverse events occurred during the previous period. Severity and relationship with intervention of these adverse events will be evaluated by two independent doctors otherwise uninvolved in the trial. Conflicts will be resolved by consensus or if not possible by consultation of a third reviewer.

Proportions of patients reporting any adverse events and serious adverse events during the whole study period, during the intervention period, and during the follow up period stratified by intervention group as randomized will be reported. Number of adverse events per patient reporting any such events will also be given as well as types/severity of events and supposed relationship with interventions.

Software

All analyses will be performed with Stata 14 (Stata Corporation, Texas, USA).

VII. REFERENCES

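### Only the exercise arm can report adverse events through the app, yet the by-arm harms summary pools all reporting routes and counts events only among patients who report one

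*SAP*

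**What the plan says.** The harms text is in SAP section 6.2, Analysis of harms. It describes three things.

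- **Unprompted reports.** For the exercise arm: "Patients in the intervention group can actively report adverse events to the responsible doctor at any time through the smart phone app", or by phone or WeChat. For controls: "Patients in the control group can actively report adverse events by contacting the responsible doctor, the clinical department, or the researcher by phone or WeChat". The app is the only difference between the two lists.
- **Scheduled questions, the same in both arms.** "all patients will be asked at 2 and 4 weeks telephone consultations, at the 6 weeks post-treatment assessment and at 24 weeks follow-up assessment" whether any event occurred in the preceding period. Severity and relationship to the intervention "will be evaluated by two independent doctors otherwise uninvolved in the trial".
- **Summary.** "Proportions of patients reporting any adverse events and serious adverse events during the whole study period, during the intervention period" and during follow-up, by arm as randomized. In addition: "Number of adverse events per patient reporting any such events will also be given", with types, severity and supposed relationship.

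The summary does not separate events by route of report. No test, interval or model is named for harms, and no expected event rate is given. Section 2.2 lists adverse events in both groups, and the safety of the programme, among the additional objectives.

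**The concern.** A by-arm table of adverse events will be read as a comparison, whether or not a test is attached. If one arm has an easier way to report, part of any difference may be a difference in detection. The app is also the treatment platform: section 3.1 delivers the programme through it, and section 4.2 times exercise from opening to closing it. Exercisers therefore have it in use regularly during the six weeks, whereas a control must decide to call or send a message. The effect would fall mainly on minor events that a patient might not recall or mention when next asked. Between weeks 6 and 24 a single question covers 18 weeks, and the SAP does not say whether app reporting continues in that time.

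The event count raises a separate problem. Patients who report any event are a subset formed after randomization, and its make-up depends on the reporting route. If the app brings in more patients with one minor event each, the mean per reporter falls while events per randomized patient rise.

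At stake is the reading of a stated safety objective. No efficacy result is involved.

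**Working it through.** **Figures available.** The SAP gives no figure for harms to reproduce. The only number taken from it is the arm size: section 3.3 has 96 evaluable patients and 20% attrition, and 96 / 0.80 = 120, or about 60 per arm.

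**Model for the proportion with any event.** True risk is set equal in both arms, so any apparent difference is detection. All three inputs are assumptions:

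- p, the true proportion with any event: 10% to 40%
- c, the share of affected patients captured by routes common to both arms (scheduled questions, phone, WeChat): 60% to 95%
- a, the share of those otherwise missed whom the app captures: 25% to 50%

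Observed control proportion = p × c. Observed exercise proportion = p × [c + (1 − c) × a]. Their ratio is 1 + a(1 − c)/c, which does not depend on p.

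| p | c | a | Control | Exercise | Difference (points) | Apparent ratio |
|---|---|---|---|---|---|---|
| 10% | 95% | 25% | 9.5% | 9.63% | 0.13 | 1.01 |
| 20% | 95% | 50% | 19.0% | 19.5% | 0.5 | 1.03 |
| 20% | 80% | 50% | 16.0% | 18.0% | 2.0 | 1.13 |
| 20% | 60% | 25% | 12.0% | 14.0% | 2.0 | 1.17 |
| 20% | 60% | 50% | 12.0% | 16.0% | 4.0 | 1.33 |
| 40% | 60% | 50% | 24.0% | 32.0% | 8.0 | 1.33 |

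Example, third row: 20% × [0.80 + 0.20 × 0.50] = 18%, against 20% × 0.80 = 16%.

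Over the whole range the ratio runs from 1.01 to 1.33 and the difference from 0.1 to 8.0 points. With a = 0, which is what restricting the comparison to the common questions does in this model, the app-related difference is zero throughout.

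The SAP plans no test. If a reader applied a two-sided 5% test with 60 per arm (normal approximation), the chance of a false excess in the exercise arm would be 2.6% to 16.2%, against a nominal 2.5% on that side.

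**Count per reporter.** Hypothetical example with 60 per arm:

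| | Reporters | Events | Per reporter | Per randomized patient |
|---|---|---|---|---|
| Arm A | 6 | 12 | 12/6 = 2.0 | 12/60 = 0.20 |
| Arm B | 20 | 24 | 24/20 = 1.2 | 24/60 = 0.40 |

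Arm A looks worse per reporter, and arm B has twice the events per randomized patient. Read alone, the planned count can rank the arms the wrong way round.

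**The case against.** The strongest reply is that the SAP already limits the problem. Every patient is asked the same question four times, and the main measure is whether a patient had any event. The app changes that measure only for a patient whose events would be missed at every relevant contact and also not reported by phone or WeChat. Where the common routes catch 95% of affected patients, the ratio is at most 1.03. The summary is descriptive, an excess in the exercise arm errs on the cautious side for safety, and serious events as section 3.5 describes them (death, related re-hospitalization) should depend little on an app. All of this stands and keeps the point modest. It does not remove it, because without the route of report nobody can tell afterwards which row of the table applied.

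On the count, events per patient can be recovered as proportion times mean count. That is correct if a mean is shown by arm, but the SAP does not specify the form of this summary. Independent rating of severity and relationship is useful but cannot add events that were never reported.

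Three stronger readings are tempting, and the SAP does not support them.

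- **Live monitoring as a second one-arm source of events.** Section 3.1 has patients "monitored remotely in real-time via a heart rate device worn on the body of the patient", but as part of the programme. Section 4.2 uses heart rate to define effective exercise time. The harms text does not list it as a route.
- **Counting app sessions as reporting occasions.** One could set 3–4 sessions × 6 weeks = 18–24 against three contacts for controls. The SAP does not say that a session prompts a question about events, and controls can call or write at any time.
- **A much larger distortion.** App-arm capture of 75% against 50% in controls, applied to a 20% risk, gives 15% against 10%, a ratio of 1.5. That holds only if the scheduled questions recover nothing. If they recover 80%, the same rates give 20% × (0.80 + 0.20 × 0.75) = 19% against 20% × (0.80 + 0.20 × 0.50) = 18%, a ratio of 1.06.

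**Conclusion.** The point holds in a limited form. The reporting routes are unequal by design, and the planned by-arm proportions pool them, so the harms comparison may be inflated in the exercise arm, chiefly for non-serious events. It is not shown that the comparison is biased to any particular degree. With equal true risk, the apparent risk ratio is about 1.01 to 1.33 under capture rates that are assumed, not documented. It is negligible if the common routes catch nearly everything and material only if they miss many events. The count per reporting patient is not a between-arm comparison on its own. This is worth correcting because safety is a stated objective and the correction is small.

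**What to change.** In section 6.2, Analysis of harms:

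1. Record the source of each event: scheduled question, app, phone or WeChat.
2. Keep the planned all-source table, and include serious events from every source.
3. Add a by-arm table of events elicited by the scheduled questions common to both arms. Count an event already reported by another route if the patient confirms it when asked; otherwise exercisers who had used the app could be undercounted. Show app and other spontaneous reports separately.
4. Report events per randomized patient, or per person-week of follow-up, beside the count per reporter.
5. State that any between-arm difference in non-serious events will be interpreted in light of the unequal routes.

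The cost is one data field, if the source is not already collected, and one further table. No new patient contact is needed. The scheduled-question table will omit some spontaneous events, so it should supplement the all-source table and not replace it.
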